
Study Objectives

Primary Objectives

The **primary objective** of this study is to evaluate the current management approach with “intermediate” or “therapeutic” doses of tinzaparin for thromboprophylaxis in hospitalized patients, non on ICU organ support, with confirmed COVID-19.

- Evaluate incidence of thrombotic events
- Evaluate incidence of bleeding events

Secondary Objectives

The **secondary objective** is to

- ✓ Examine the course of illness of COVID-19 via measure of clinical improvement and/or survival, assessed at pre-specified time points post admission

Patients demographic & somatometric data, medical history (thrombosis & bleedings related history, co-morbidities, chronic use of medications, results of laboratory tests etc.), clinical parameters, anticoagulant prophylaxis dose & duration, efficacy (thrombosis events), safety (bleedings), imaging and laboratory tests results and information about other supportive treatment will be recorded; more than one outcomes could be recorded.

Based on analysis of collected data, **we'll examine correlations between thromboprophylaxis approach, patients' profiles and clinical outcomes.**

Study Endpoints

Primary Endpoints

- **Incidence of thrombotic events** (total & per type e.g. PE, DVT, symptomatic, incidental, proximal, distant etc.)
- **Incidence of bleeding events** (total & per type e.g. Major, CRNMB and minor)

Secondary Endpoint

- **World Health Organization (WHO) progression scale** (range from 0 (healthy) to 10 (death); values below or equal to 5 correspond to the absence of any oxygen supply beside nasal or facial mask)
- **Length of hospital stay (days)**

Study Design

This is a retrospective phase IV, observational, non-interventional cohort study that aims to collect data regarding thromboprophylaxis management in high thrombotic risk hospitalized, non on ICU, patients with COVID-19 pneumonia. Specifically, we will collect retrospectively data for patients received thromboprophylaxis with tinzaparin, according to current clinical practice, during hospitalization, for one year before the study initiation date, to evaluate safety and efficacy of thromboprophylaxis and to examine possible associations of

patients' profiles with thrombotic and bleeding events and the course of illness in this cohort of patients.

We will collect data retrospectively in paper CRFs, recorded from the treating physicians.

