Additionally, we will assess the association of a panel of laboratory and clinical parameters representing an inflammatory and hemostatic state with VTE and bleeding events and clinical outcomes.

Institutional Review Board will approve the study.

Basic/common markers/parameters

- ✓ *D-Dimers*
- ✓ *C-reactive protein (CRP)*
- ✓ *hemoglobin*
- ✓ *platelets count*
- ✓ *ferritin*
- ✓ *fibrinogen*
- ✓ *SpO₂ in FiO₂ 21%*

In all cases, laboratory and clinical parameters will be collected at 3 time points: at admission/baseline, after one week and at discharge.

Subject Population

Key criteria for Inclusion and Exclusion

Inclusion Criteria

1. Patients admitted to hospital with COVID-19, PCR+ SARS-CoV-2 infection (from any specimen) administered thromboprophylaxis with tinzaparin in intermediate or therapeutic dose
2. Age \geq 18 years
3. Signed informed consent

Exclusion Criteria

1. Patients admitted to ICU with COVID-19, PCR+ SARS-CoV-2 infection (from any specimen)
 2. Age < 18 years
 3. Pregnancy
 4. Current diagnosis or suspicion of pulmonary thromboembolism or deep vein thrombosis
 5. Progression to death was imminent and inevitable within 24 hours from the admission, irrespective of the provision of treatments
 6. Not signed informed consent
-

Study Phases**Screening**

(1) Screening: screening patient files for eligibility, obtaining consent, If eligible

All the data will be gathered from medical records by chart review of the individual patients in a retrospective fashion. There will no direct patient interaction in the study.

Data collection

- Demographic data collection (Gender, Date of birth, Weight, Height, etc.)
- Medical history & pathologic features (Thrombosis & bleedings related history, risk factors, recent surgery, co-morbidities, chronic use of medications, results of laboratory tests, clinical parameters etc.)
- Anti-coagulant administration data
- Thrombotic & bleeding events during course of hospitalization
- Other adverse events related to anticoagulation
- Clinical improvement and/or survival during hospitalization

Timepoints of evaluation

Data of Covid-19 pneumonia patients retrospectively enrolled in the study will be evaluated on a regular basis following the Baseline Visit;

Visit 1 – Baseline, at admission;

Visit 2 - will be after 1 week \pm 2 days

Visit 3 - will be by at discharge from hospital

Statistical analysis & report**Statistical analysis****Statistical and Analytic Plan**

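### Signed consent is a condition of entry when past files are screened, but the criteria give no route for patients who died; if they enter less readily than survivors, mortality and fatal events are understated.

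*Combined protocol and SAP*

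**What the plan says.** The study is retrospective. Under Study Design, data are taken from stays "for one year before the study initiation date". Under Study Phases, the screening step reads "1) Screening: screening patient files for eligibility, obtaining consent, If eligible". Inclusion criterion 3 is "Signed informed consent" and exclusion criterion 6 is "Not signed informed consent". Neither says who may sign, and neither mentions a representative or a waiver. The Screening text also states "There will no direct patient interaction in the study". Ethics board approval is planned, with no detail on consent.

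Death is among the outcomes:

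- Survival is part of the secondary objective, and the Data collection list includes "Clinical improvement and/or survival during hospitalization".
- The WHO progression scale, a secondary endpoint, scores death as 10.
- Efficacy Evaluations defines fatal PE, including certain unexplained deaths.
- Safety Evaluations counts bleeding that contributes to death as major bleeding, a named type within a primary endpoint. Neither mortality nor fatal PE is itself named under Study Endpoints.

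Two exclusions remove some deaths by design. Exclusion 5 applies where "Progression to death was imminent and inevitable within 24 hours from the admission". Exclusion 1 removes patients admitted to ICU, without saying whether this covers transfer later in the stay. The last evaluation, Visit 3, "will be by at discharge from hospital".

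**The concern.** Consent is sought after the stay, when it is normally already known whether the patient died. A patient who died cannot sign. Applied as written, with no alternative route in the criteria, exclusion 6 makes entry depend on an outcome that the study measures. Ward deaths that exclusions 1 and 5 do not remove belong to the target population, so losing them is selection bias and not a restriction made by design.

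At stake are the survival results, the top category of the WHO scale, fatal PE and fatal bleeding. The 95% confidence intervals planned under Clinical Study Report reflect sampling error only and would not show the loss. No record of eligible but non-enrolled patients is described. A complete absence of deaths would be visible in the results; a partial loss would not.

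**Working it through.** The documents state no sample size, consent rate, event rate or mortality for the eligible population, so there is no figure of the plan's own to reproduce. The 25% to 40% mortality under Study Rationale concerns ICU organ-support cohorts, which are outside this population, and is not used. Every input below is an assumption.

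**Mortality.** Let d be true in-hospital mortality among otherwise eligible patients, and r the probability that a deceased patient enters divided by that for a survivor.

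Observed mortality = d·r / [(1 − d) + d·r]

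For d = 5% and r = 0.5: 0.025 / (0.95 + 0.025) = 0.025 / 0.975 = 2.56%.

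| True d | r = 0 | r = 0.25 | r = 0.5 | r = 0.75 | r = 1 | r = 1.25 |
|---|---|---|---|---|---|---|
| 2% | 0 | 0.51% | 1.01% | 1.51% | 2.0% | 2.49% |
| 5% | 0 | 1.30% | 2.56% | 3.80% | 5.0% | 6.17% |
| 10% | 0 | 2.70% | 5.26% | 7.69% | 10.0% | 12.2% |

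Mortality is understated for every r below 1 and overstated for every r above 1. Setting observed mortality to 0.9·d gives r = 0.9(1 − d) / (1 − 0.9d), which is 0.898, 0.895 and 0.890 for d = 2%, 5% and 10%. Understatement therefore stays within 10% of the true value only if r is at least about 0.9.

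**A fatal event.** With true incidence f, observed incidence = f·r / [(1 − d) + d·r]. For f = 1% and d = 5%, it is 0.76% at r = 0.75, 0.51% at r = 0.5 and 0 at r = 0.

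**Would the interval reveal it?** Wilson 95% intervals, with true d = 5%:

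| Enrolled | r | Deaths seen | 95% CI | Contains 5%? |
|---|---|---|---|---|
| 500 | 0.5 | 13 | 1.5% to 4.4% | No |
| 300 | 0.5 | 8 | 1.4% to 5.2% | Yes |
| 200 | 0.5 | 5 | 1.1% to 5.7% | Yes |
| 500 | 0.75 | 19 | 2.4% to 5.9% | Yes |

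Whether the interval misses the truth depends on the assumed n and r.

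**Total thrombotic or bleeding incidence.** Let RR be the event risk in those who died relative to survivors.

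Relative bias = {[(1 − d) + d·r·RR] / [(1 − d) + d·r]} / [(1 − d) + d·RR] − 1

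For d = 5%, r = 0.5 and RR = 2: (1.000 / 0.975) / 1.05 − 1 = −2.3%. For RR = 0.5, 1 and 3 the bias is +1.2%, 0 and −4.4%. At r = 0 it is −4.8% for RR = 2 and −9.1% for RR = 3. Both direction and size depend on RR, which the documents do not give.

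**The case against.** The strongest objection is that this is an absence claim where text is missing. The document is a synopsis, its consent pages are not in the text available here, and those pages are where a representative's signature or a waiver would normally be set out. Inclusion 3 does not say that the patient must be the signatory, and an ethics board is to approve the study. This stands in part: it cannot be said that no route exists. But the criteria are what sites apply, they contain no exception, and a statement that a board will approve the study does not alter exclusion 6.

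A reader might infer that no deceased patient can enter. That follows only if the patient alone may sign, which the documents do not state. Nor is the direction certain. If the no-interaction statement is taken literally, survivors cannot sign in person either, and relative capture is unknown. A waiver for the deceased alone, with some survivors refusing, would put r above 1.

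A reader might also infer that the primary incidence totals are materially biased. The documents do not show that event risk differs between those who died and survivors, and under the moderate assumptions above the effect is a few per cent in relative terms.

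Finally, ICU patients are excluded, so eligible deaths may be few. That stands as to number, but not as to proportion: at d = 2%, r = 0.5 still gives about half the true mortality. The caution under Statistical and Analytic Plan that correlations serve only to assess hypotheses does not cover descriptive survival and incidence figures.

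**Conclusion.** The concern holds as a conditional one. The entry rule as written makes inclusion depend on obtaining a signature after the outcome, and the criteria give no route for those who died. If r is below 1, in-hospital mortality, WHO score 10, fatal PE and bleeding that contributes to death are understated; if only the patient may sign, they are absent. Under an assumed true mortality of 5%, the observed figure is 3.8% at r = 0.75, 2.6% at r = 0.5 and 0 at r = 0, and the bias reverses above r = 1.

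The conclusion covers ward deaths not removed by exclusion 1 or 5; how many these are depends on the unclear reach of the ICU exclusion. It does not extend to a demonstrated bias in total thrombotic or bleeding incidence, or to a claim that the planned intervals would necessarily exclude the truth. It should be fixed; confidence is moderate because the consent pages could not be read.

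**What to change.** First check the consent documents. Unless they already provide a route, amend inclusion 3 and exclusion 6 so that otherwise eligible deceased patients enter under an ethics-approved waiver for chart review, or under representative consent if the board requires it. State who may sign, and reconcile this with "There will no direct patient interaction in the study". If a route already exists, refer to it in the criteria.

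Keep a screening log of all eligible patients, enrolled and not enrolled, by vital status at the end of the stay, and report those counts. Where the board permits anonymous counts, compute mortality over all eligible patients, counting both non-enrolled deaths and non-enrolled survivors. Assumed example: 1000 eligible, 50 deaths, 80% of survivors and 40% of deceased patients enrolled. Enrolled are 950 × 0.8 = 760 survivors and 50 × 0.4 = 20 deaths, so the cohort shows 20/780 = 2.6%. Non-enrolled are 30 deaths and 190 survivors, giving (20 + 30) / (780 + 30 + 190) = 50/1000 = 5.0%. Adding only the deaths would give 50/810 = 6.2%, which overstates mortality.

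If no route is available, restrict conclusions to consenting patients, report the number of eligible deaths not enrolled if permitted, and do not present observed survival or fatal-event rates as cohort estimates.

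The cost is one amendment, an ethics request, a small log at each site and possibly contact with families. Whether a waiver or anonymous counts are allowed is for the ethics board.

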Descriptional statistical analysis will be performed for all study data along with epidemiology methods. Categorical data will be analyzed using the *chi-square* and *Fisher exact test*. Continuous variables will be reported as mean and standard deviations (SD) and will be analyzed using the *t-test* analysis. An unadjusted odds ratio (OR) will be calculated using a *Cochran-Mantel-Haenszel test*. To determine the impact of potential effect modifiers a *logistic regression model* will be used to calculate the adjusted odds ratio. For more complex correlations (i.e. inferential statistics) we will use, among other methods, *chi-square* or *Fisher exact tests*, *ANOVA*, *Mann-Whitney U tests* and *t-tests*, according to the data properties and in order to evaluate the relationships between different patient and disease characteristics with the primary and secondary study outcomes, such as:

- ✓ *Number of patients enrolled*
- ✓ *Co-morbidities*
- ✓ *Thrombosis risk factors*
- ✓ *Laboratory parameters*
- ✓ *Clinical parameters*
- ✓ *Type and duration of thromboprophylaxis therapy*
- ✓ *Therapy outcomes*
- ✓ *Thromboprophylaxis related complications*

and to present them, accordingly.

Due to the fact that this is an observational study the results of all correlations will be carefully discussed and will be used only to assess hypotheses.

Finally and depending on the collected data multivariate analysis may be performed in order to reveal confounding factors.

Clinical Study Report (CSR)

Analyzed parameters will be presented with standards statistical measures (mean values, median values, ranges, quartiles, percentages etc.) and the results will be presented accordingly into tables and informative plots.

A p-value of less than 0.05 will be considered statistically significant and all values will be reported with a 95% confidence interval (CI).

Study Registration

Study will be registered in

NIH, U.S. National Library of Medicine, Clinical Trials database of privately and publicly funded clinical studies, <https://clinicaltrials.gov/ct2/home>

Efficacy Evaluations

- ***Symptomatic/Suspected vein thromboembolism, including pulmonary embolism and deep vein thrombosis***

Confirmation of symptomatic PE requires symptoms of PE and one of the following findings

1. *A (new) intraluminal filling defect in (sub) segmental or more proximal branches on spiral CT scan or on MRI scan;*

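### Adjusted odds ratios are planned for thrombotic and bleeding events, which the endpoints split by type, with no method for outcomes that have few events

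*Combined protocol and SAP*

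**What the plan says.** The combined protocol and SAP is a synopsis, and the analysis is set out under Statistical analysis & report, Statistical and Analytic Plan.

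- **The commitment.** The sentence opens "To determine the impact of potential effect modifiers a" and continues that a logistic regression model "will be used to calculate the adjusted odds ratio". The wording is firm. It names no outcome, covariates or estimator, and it does not say what happens if the model cannot be fitted.
- **The optional layer.** A later sentence adds that "depending on the collected data multivariate analysis may be performed in order to reveal confounding factors". This is conditional and carries no rule.
- **The outcomes.** Study Endpoints lists thrombotic events and bleeding events as primary, each in total and by type: for example PE, DVT, symptomatic, incidental and proximal events, and major, clinically relevant non-major and minor bleeding. These are the naturally binary endpoints, so I read the odds ratios as applying to them.
- **The candidate predictors.** Under Study Design the plan will "assess the association of a panel of laboratory and clinical parameters representing an inflammatory and hemostatic state with VTE and bleeding events". Seven markers are named, and "laboratory and clinical parameters will be collected at 3 time points". The history items under Data collection are open-ended.
- **Small counts.** Fisher's exact test is offered for categorical data. Nothing equivalent is offered for the adjusted analysis.
- **Size.** The documents give no sample size, number of sites, expected incidence or event count.

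**The concern.** Logistic regression is sensitive to the number of events in relation to the number of terms. When events are few, some combination of covariates may separate patients with the event from those without it. Maximum likelihood then has no finite solution. Short of that point, its odds ratios tend to lie too far from 1 and the intervals are very wide. The plan foresees small counts in its two-way tables but not in its models.

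Splitting the endpoints by type makes small counts plausible for some of them, whatever the totals turn out to be. Without a rule set in advance, the analyst would have to drop covariates until a model converges, after seeing the data. The reported adjusted odds ratio would then depend partly on that search, yet it would still carry a 95% confidence interval and be judged at p below 0.05.

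**Working it through.** The plan has no figure of its own to reproduce, so the check asks how the default fit behaves over a range of event counts.

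**Events and events per term.** Events = N × rate, and events per term = events / k. Every N and rate here is an assumption.

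- 9 events: for example 300 × 3%. With k = 12, 9/12 = 0.75 per term.
- 15 events: 300 × 5%. With k = 12, 15/12 = 1.25 per term.
- 50 events: 1000 × 5% or 500 × 10%. With k = 12, 50/12 = 4.2 per term.

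**Simulation with 12 terms.** The true dose-group odds ratio is 2.0. The model was run under two sets of covariate assumptions. In set A the terms are dose group, four co-morbidities and seven markers, with 800 data sets per scenario; a failed fit means non-convergence or a coefficient above 8 in absolute value. ML = maximum likelihood. ML odds ratios are geometric means over the fits that succeeded.

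| Events | Set | ML fails | ML odds ratio | Firth odds ratio |
|---|---|---|---|---|
| about 9 | A | 52% | 2.35 | 2.03 |
| 9 | B | 33% | 2.43 | 1.95 |
| 15 | A | 26% | 2.24 | 2.03 |
| 15 | B | 7% | 2.34 | 2.03 |
| 18 | A | 16% | 2.29 | 2.10 |
| 30 | A | 4% | 2.12 | 2.02 |

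In set A the Firth figure covers all data sets, so the two columns are not strictly comparable. In set B both methods are compared on the same data sets. There the root mean squared error of Firth was never larger than that of ML, and the two nearly agree from 50 events.

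Overstatement at 9 and 15 events runs from 2.24/2.0 = 1.12 to 2.43/2.0 = 1.22, that is 12% to 22%. The Monte Carlo standard error of the 26% is √(0.26 × 0.74 / 800) = 1.6 percentage points. Noise in that figure therefore does not explain the gap between 26% and 7%; the covariate assumptions do.

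**Does it depend on 12 terms?** Models with 7 and 15 terms were run with 300 data sets per cell. The assumptions were independent covariates, dose groups split 50/50 with odds ratio 2, binary covariates at 20% prevalence with odds ratio 1.5, and continuous covariates with odds ratio 1.3 per SD.

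| Events | k | ML fails | ML odds ratio | Firth odds ratio |
|---|---|---|---|---|
| 10 | 15 | 33-36% | 2.08-2.28 | 1.91-2.05 |
| 15 | 15 | 11-13% | 2.39-2.46 | 1.84-2.00 |
| 50 | 15 | 0% | 2.02-2.06 | 1.95-1.96 |
| 10 | 7 | 12-14% | 2.07-2.27 | 1.99-2.06 |
| 15 | 7 | about 5% | 2.17-2.27 | 2.05-2.06 |
| 25 | 7 | 0% | 2.03 | 1.94 |
| 50 | 7 | 0% | 2.01-2.08 | 1.96-2.04 |

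**At the very bottom.** With 3 events or fewer, ML fails in 96-100% of data sets for 15 terms and 71-90% for 7. The surviving 7-term ML fits give 0.92-1.62, below the true 2.0. For 15 terms Firth converged in only 67-80% of data sets within the iteration limit used, and gave 1.40-1.53. Penalisation does not rescue that case, so a rule for giving no adjusted odds ratio is also needed.

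**The case against.** The strongest reply is that the plan is silent and has not chosen a wrong method. A Firth fit is also a logistic regression model, so the fix is compatible with the present wording. That is correct: maximum likelihood is the usual default, not something the plan states. The gap remains, because silence leaves the default in place.

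A reader might infer more than the documents support in five ways:

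- **That events are known to be rare.** No rate is given. Study Design calls the cohort high thrombotic risk, incidental thromboses count, and bleeding includes minor bleeding. Totals could reach the range where the default fit is sound.
- **That the bulleted list is the logistic model's covariate set.** It follows a different sentence, on chi-square, Fisher, ANOVA, Mann-Whitney and t-tests used "in order to evaluate the relationships between different patient and disease characteristics with the primary and secondary study outcomes". Some bullets, such as enrolment and therapy outcomes, could not be covariates at all.
- **That the odds ratio is always overstated.** At 3 events or fewer the main result is no fit, and surviving estimates can be too low.
- **That missing markers would remove most patients.** The plan states neither a model with all seven markers nor any rate or pattern of missing values, so no figure can be given.
- **That adjusted odds ratios are definitely planned for every type.** The endpoints are split by type, but the logistic sentence does not say how far down it goes.

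Two further points carry weight. The primary endpoints are incidences, which this does not touch, and the plan says that correlations serve only to assess hypotheses. Also, a term limit alone removes much of the problem: 7 terms at 25 events fit without trouble by maximum likelihood. At 15 events, however, a 7-term ML model still fails in about 5% of data sets and gives 2.17-2.27 against 2.05-2.06 with Firth.

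**Conclusion.** The point holds as an inexpensive improvement to the adjusted analysis. It is not a flaw in the primary incidence estimates. The plan commits to adjusted odds ratios and has no method for sparse outcomes, while its own endpoint definitions divide the events into small categories.

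The size depends on event counts that the documents do not give. For an assumed 12-term model with a true odds ratio of 2.0, the default fit fails in about 7-26% of data sets at 15 events and 33-52% at about 9. Where it fits, it gives about 2.2-2.4. At 50 or more events it agrees closely with Firth and nothing is lost. The failure percentages shift with the assumed covariates. The direction of the result at 9 to 15 events is the same under both sets of assumptions.

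**What to change.** Amend the Statistical and Analytic Plan, before the outcome data are examined, to say:

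1. Adjusted odds ratios for thrombotic and bleeding events are fitted by Firth penalised logistic regression with profile-likelihood confidence intervals.
2. The number of model terms is limited by the observed number of events, using a stated ratio. One term per 5 to 10 events, for example, would allow at most 15/5 = 3 terms at 15 events and 50/5 = 10 at 50. Name the covariates in order of priority for each outcome, so that the limit decides which enter.
3. The event count is printed beside every odds ratio.
4. For any type with too few events under that ratio, only the incidence with an exact 95% confidence interval is given, and no adjusted odds ratio.

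The cost is a few lines of SAP text and standard software, with no new data. The downside is fewer covariates per model, hence less adjustment for confounding, and no adjusted odds ratio for the rarest types. If events prove plentiful, Firth and maximum likelihood give nearly the same answer, so little is lost.

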Introduction	
International guidelines recommend that hospitalized patients with COVID-19 should receive pharmacological prophylaxis against VTE, in the absence of contraindications [7,8,9]. With respect to how VTE prophylaxis is achieved, Low Molecular Weight Heparins (LMWH), in addition to their well-known anticoagulant properties, appear to have additional antiviral and anti-inflammatory effects that may be potentially beneficial in hospitalized COVID-19 patients. [10,11].
 
Though international and national guidelines states that all hospitalized patients with COVID-19 should receive pharmacologic thromboprophylaxis, the rising incidence of thrombotic complications in COVID-19 patients has led a lot of hospitals to adopt the strategy of increasing the dose of anticoagulation for prophylaxis to 'intermediate' or "therapeutic" doses using a risk-adapted strategy with increased doses administration based on factors associated with increased risk; clinicians weigh the benefits and risks of therapeutic anticoagulation in terms of thrombosis and major bleeding risk for individual patients.
 
Additionally, LMWHs have different physiochemical characteristics as a result of the diverse methods of their manufacturing. The variations in molecular composition and pharmacological properties of LMWHs are reflected in differences in their clinical efficacy and safety. Each LMWH should, therefore, be considered as a unique substance. Tinzaparin is the only LMWH known that is prepared by enzymatic hydrolysis with heparinase [12,13,14,15]. Due to its preparation method, tinzaparin has distinct properties than other LMWHs including and not limited to: higher Anti-IIa activity and Anti-Xa/Anti-IIa activity ratio, higher release of Tissue Factor Pathway Inhibitor (TFPI), less dependence from renal function for its clearance and more complete neutralization from its antidote, if needed. Due to the key role of increased Thrombin generation (IIa) and Tissue factor (TF) pathway activation in COVID-19-associated thrombosis [16], special properties of tinzaparin in Anti-IIa activity and TFPI production and release from endothelial cells, as well as significant effects of TFPI in various vascular, inflammatory, cardiovascular, hematological and oncological disorders [17,18,19,20,21], tinzaparin could have an expanded role beyond its well-known anticoagulant function.
 
The purpose of this study is to evaluate the overall clinical effectiveness and safety of 'intermediate' or "therapeutic" doses anticoagulation with tinzaparin administered for thromboprophylaxis in COVID-19 patients with moderate disease severity during hospitalization in Greek hospitals.

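### The plan does not tie the WHO progression analysis to the admission score, so severity at admission can appear as an association with tinzaparin dose.

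*Combined protocol and SAP*

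**What the plan says.** The Secondary Objectives section sets one aim: "Examine the course of illness of COVID-19 via measure of clinical improvement and/or survival, assessed at pre-specified time points post admission". Its measure is the WHO progression scale, an ordinal scale from 0 to 10 with death at 10. No analysis time point or summary measure is fixed for it. The Study Objectives add that "we'll examine correlations between thromboprophylaxis approach, patients' profiles and clinical outcomes".

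The Statistical and Analytic Plan introduces the methods with "For more complex correlations (i.e. inferential statistics) we will use, among other methods". It then names chi-square or Fisher tests, ANOVA, Mann-Whitney and t-tests, to be chosen by the properties of the data and used "in order to evaluate the relationships between different patient and disease characteristics with the primary and secondary study outcomes". Type and duration of thromboprophylaxis is one of the listed characteristics.

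Two sentences concern adjustment. A logistic model, framed around effect modifiers, "will be used to calculate the adjusted odds ratio"; it lists no covariates. Depending on the data, "multivariate analysis may be performed in order to reveal confounding factors"; again no covariates are named.

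On the choice of dose, the Introduction says that many hospitals moved to higher doses "using a risk-adapted strategy with increased doses administration based on factors associated with increased risk". Clinical parameters are collected at admission, at one week and at discharge, but an admission WHO score is not listed explicitly.

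**The concern.** Course after admission depends on where the patient started. A comparison of later WHO scores between dose groups, made without the admission score, cannot separate a patient who started sicker from one who got worse. That would matter less if dose were unrelated to severity. Here the protocol's own account is that dose follows risk, so the groups may well differ at admission.

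At stake is the dose comparison on the WHO scale. An association below the plan's 0.05 threshold could reflect who was given the higher dose, and a real difference in the other direction could be hidden.

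**Working it through.** **No figure to reproduce.** The documents give no sample size, effect size, dose split, baseline imbalance or correlation between admission and later score. Everything below rests on assumed values and shows a range. A two-sided 5% level is assumed, because the plan does not state sidedness.

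**Formula.** Let ρ be the correlation between admission and follow-up score, and d the difference in mean admission score between dose groups, in SD units. With no dose effect, the unadjusted comparison is biased by ρ × d SD. With N patients in two equal groups the standard error is 2/√N, so the shift in the test statistic is ρd√N/2. The rejection rate is Φ(shift − 1.96) + Φ(−shift − 1.96).

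**Moderate disease only (admission scores 4 and 5).** Assume half the patients at each score.

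- If 40% of those at 4 and 60% of those at 5 get the higher dose, the share at 5 is 60% in the higher-dose group and 40% in the lower. The difference is 0.2 and the SD is 0.5, so d = 0.2/0.5 = 0.4.
- If the shares are 30% and 70%, d = 0.4/0.5 = 0.8.

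| N | ρ | d | shift | formula | simulated Mann-Whitney |
|---|---|---|---|---|---|
| 300 | 0.20 | 0.4 | 0.69 | 11% | 11% |
| 300 | 0.20 | 0.8 | 1.39 | 28% | 29% |
| 300 | 0.38 | 0.4 | 1.32 | 26% | 26% |
| 300 | 0.38 | 0.8 | 2.63 | 75% | 75% |

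The simulations used 1000 runs per cell. At N = 150 the same four cells run from 8% to 45%. The test adjusted for the admission score rejects in 4 to 6% throughout.

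**Low end.** With scores 4 and 5 only, N = 100, weaker dependence on the admission score (a log-odds slope of 1.0 per level) and the higher dose in 40% versus 50%, the rate is 5%. With a slope of 1.5 it is 6%.

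**Wider severity range (scores 4, 5 and 6).**

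- With N = 300 and the higher dose in 30%, 50% and 70% by score, Mann-Whitney rejects in 68 to 70% of runs. With 40%, 50% and 60% it rejects in 25 to 26%. The adjusted test rejects in 5 to 6%.
- In a separate set-up with 100 per group and admission scores split 30/60/10% versus 10/60/30%, Mann-Whitney rejects in 14%, 32% and 54% of runs under weak, moderate and strong dependence on baseline. Rank ANCOVA with the admission score rejects in 4 to 5.5%.
- An unadjusted change score is not a reliable cure: in the same three cells it rejects in 36%, 16% and 6%.
- When the groups have the same admission distribution, the unadjusted and adjusted tests both stay near 5%.

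**Precision.** The variance ratio, adjusted to unadjusted, is (1 − ρ²)/(1 − r²) with r² = d²/(d² + 4).

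- Balanced groups (d = 0): the ratio is 0.96 at ρ = 0.2, 0.91 at 0.3 and 0.75 at 0.5. For an assumed 0.5 SD effect and 63 per group, power moves from about 80% to about 82%, 84% and 90%.
- Strong imbalance (d = 1, so r² = 1/5 = 0.2): the ratio is 0.96/0.8 = 1.20 at ρ = 0.2 and 0.91/0.8 = 1.14 at ρ = 0.3. Adjustment then costs precision.

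**The case against.** The best defence is that the plan leaves something unspecified and does not choose a wrong method. The list of tests is open, an adjusted odds ratio is firmly planned and a multivariate analysis is foreseen. Nothing says that the tests apply to a raw score at one visit; a Mann-Whitney test can be run on change. The study aims at moderate disease, which is 4 to 5 on the scale, and this narrows the admission range. The endpoint is secondary, and correlations serve only to assess hypotheses.

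Much of this stands. A reader might infer that the plan rules out using the admission score, or that it prescribes means and t-tests for an ordinal scale. It does neither: the gap is an omission, and the WHO scale is never classed as continuous. A reader might also infer that power is being lost. The documents make no power claim and give no inputs for one. Any gain from adjustment is small at low correlation and can reverse under strong imbalance.

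The defence does not close the gap. The logistic model names neither the WHO scale nor any covariate. The multivariate analysis depends on the data, and an open list leaves the choice until the data are seen. The inclusion criteria set no WHO limit, and restricting admission to scores 4 and 5 still gives rates up to 75% when dose follows severity strongly. A hypothesis produced by admission severity would mislead even in an exploratory study.

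**Conclusion.** The concern holds as a risk of confounding in the dose comparison on the WHO scale. Under assumed inputs the false-positive rate of the unadjusted test runs from about 5% to about 75%. Where this study would fall cannot be told from the documents.

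It would go too far to say that admission severity will be reported as a dose effect. That needs both an admission difference between dose groups and a correlation with the later score, and the documents report neither. The Introduction says that dose follows risk factors; it does not say that dose follows oxygen need.

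The 4 to 6% after adjustment is also a best case, because the admission score was the only confounder simulated. Other reasons for choosing a dose would remain. For patient-profile associations, an unadjusted description is a legitimate aim, so the point concerns the dose comparisons. Precision is a secondary matter.

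**What to change.** In the Statistical and Analytic Plan:

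1. State that the WHO score is recorded, or derived from the chart, at Visit 1.
2. For dose comparisons, make the main WHO analysis a proportional-odds model of the week-1 score with death = 10. Adjust for the admission WHO score as a categorical covariate and for named severity and risk factors already collected. Week 1 is suggested because at discharge survivors and deaths sit near opposite ends of the scale, so admission status is likely to matter most at week 1; this is a judgement.
3. Report the common odds ratio with its 95% CI, and a cross-table of admission by week-1 category to describe improvement.
4. Keep the discharge score and the simple unadjusted tests as descriptive.
5. State that residual confounding by indication remains.

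The cost is SAP wording, one standard model and, if it is absent, one derived admission item on the CRF.
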